#### **Anticoagulants**

Patients who require therapeutic anticoagulant therapy with oral vitamin K antagonists are ineligible for enrollment; low-dose anticoagulants for maintenance of patency of central venous access device or prevention of deep venous thrombosis is allowed; therapeutic use of low molecular weight heparin (or similar parenteral drug) for venous-thromboembolic disease is allowed.

#### **Steroids**

If clinically indicated, short ( $\leq 7$  days) courses of steroids, such as dexamethasone, are allowed for patients with vestibular schwannomas and sudden-onset, transient hearing loss on protocol therapy. All such treatments must be documented in the clinical chart and study records.

### **7.4 Visit Schedule and Assessments**

Visit schedule and required on-study evaluations are outlined below:

### 7.4.1 Visit schedule

**Table 3-4 Evaluation and visit schedule**

Examination	Baseline	Day†	Week			Cycle (each cycle is 28 days)											
			1	2	3	2	3	4	5	6	7	8	9	10	11	12	
Informed consent	X																
Inclusion/exclusion criteria	X																
Vital signs	X	X	X	X	X	X	X	X	X	X	X	X	X	X	X	X	X
Physical examination	X	X	X	X	X	X	X	X	X	X	X	X	X	X	X	X	X
Performance status	X	X	X	X	X	X	X	X	X	X	X	X	X	X	X	X	X
NFTI-QOL#	X								X								
ECG	X																
MRI‡	X					X			X			X					X
Audiogram*	X					X			X			X					X
INR	X																
Free T4/TSH	X	X			X	X	X	X	X	X	X	X	X	X	X	X	X
Serum pregnancy test**	X	X			X	X	X	X	X	X	X	X	X	X	X	X	X
CBC, diff., comprehensive metabolic panel, Mg, Phos	X	X	X	X	X	X	X	X	X	X	X	X	X	X	X	X	X
Urinalysis	X	X	X	X	X	X	X	X	X	X	X	X	X	X	X	X	X

† Includes drug dispensing and repeat baseline evaluations if time between first screening and dispensing exceeds 4 weeks. Otherwise, Day 1 not performed.

# Only in adult patients ≥18 years of age

‡ Should be performed at the end of cycle

\*Should be performed at the end of cycle. Not required for patients with no measurable hearing

\*\*Required for women of childbearing potential within 7 days of starting axitinib

*Additional treatment cycles beyond 12, if applicable, will continue according to the same schedule.*

### 7.4.2 Efficacy assessments

Primary efficacy endpoint is best radiographic tumor response (i.e. maximum tumor shrinkage) during the first 12 cycles of treatment; secondary efficacy endpoint is audiologic response, as defined by the following **Response Criteria**, which were chosen based on recently published recommendations for NF2 clinical trials:

**Primary:** *Radiographic response:* for study purposes, a  $\geq 20\%$  reduction in tumor volume in any of the target tumors will constitute a partial response (PR). Complete disappearance of any of the target tumors will constitute a complete response (CR).

**Secondary:** *Audiologic response:* improvement in speech discrimination score (SDS), defined as an improvement in the score above the 95% critical difference threshold, compared to baseline audiogram at initiation of treatment. *Audiologic worsening:* decrease in SDS score below the 95% critical difference threshold, compared to baseline audiogram at initiation of treatment.

MRI of the brain and spine (in patients with spinal tumors with medically relevant or symptomatic lesions) with 3D tumor volumetrics will be performed every 3 months. Patients with vestibular schwannomas will receive baseline audiograms within 28 days before enrollment and subsequent audiograms at the time of each MRI. If an objective response, defined as a 20% reduction in tumor volume compared to baseline is observed in any target tumor or stable disease in all target tumors (i.e. less than 20% increase in size), Axitinib will be continued. Therapy will be discontinued if the **primary** target tumor enlarges by 20%. **All additional target tumors will be monitored for growth or response, but any progression in those tumors will not trigger discontinuation of therapy.** Audiologic responses will be determined, but will not be used as primary response criteria.

### 7.4.3 Treatment compliance

Records of study medication used, dosages administered, and intervals between visits will be recorded during the study. Drug accountability will be noted and patients will be asked to return all unused study medication.

### 7.4.4 Safety assessments

Safety assessments will consist of monitoring and recording all adverse events and serious adverse events, the regular monitoring of hematology, blood chemistry and urine values, regular measurement of vital signs and the performance of physical examinations.

These assessments should be performed within  $\pm 2$  days of the scheduled day of assessment except for adverse events that will be evaluated continuously through the study. Safety and tolerability will be assessed according to the NIH/NCI Common Toxicity Criteria (CTC)([http://evs.nci.nih.gov/ftp1/CTCAE/CTCAE\\_4.03\\_2010-06-14\\_QuickReference\\_8.5x11.pdf](http://evs.nci.nih.gov/ftp1/CTCAE/CTCAE_4.03_2010-06-14_QuickReference_8.5x11.pdf)).

Patients who will discontinue study treatment for any reasons are to be followed until one of the following occurs:

- Thirty days after the last dose of axitinib or until any significant drug-related toxicity resolves, whichever is longer;
- Death;
- Lost to follow-up after at least two reasonable attempts to contact the patient have been made;

- Withdrawal of consent for any further data collection or submission;
- Initiation of any other disease-directed treatment for NF2-related tumors

#### **7.4.4.1 Adverse events**

Information about all adverse events (AEs), whether volunteered by the subject, discovered by investigator questioning, or detected through physical examination, laboratory test or other means, will be collected and recorded and followed as appropriate.

An adverse event is the appearance or worsening of any undesirable sign, symptom, or medical condition occurring after starting the study drug even if the event is not considered to be related to study drug. Medical conditions/diseases present before starting study drug are only considered adverse events if they worsen after starting study drug. Abnormal laboratory values or test results constitute adverse events only if they induce clinical signs or symptoms, are considered clinically significant, or require therapy.

The occurrence of adverse events should be sought by non-directive questioning of the patient at each visit during the study. Adverse events also may be detected when they are volunteered by the patient during or between visits or through physical examination, laboratory test, or other assessments. As far as possible, each adverse event should be evaluated to determine:

1. the severity grade (mild, moderate, severe) or (grade 1–4)
2. its relationship to the study drug(s) (suspected/not suspected)
3. its duration (start and end dates or if continuing at final exam)
4. action taken (no action taken; study drug dosage adjusted/temporarily interrupted; study drug permanently discontinued due to this adverse event; concomitant medication taken; non-drug therapy given; hospitalization/prolonged hospitalization)
5. whether it constitutes a serious adverse event (SAE)

All adverse events should be treated appropriately. Such treatment may include changes in study drug treatment including possible interruption or discontinuation, starting or stopping concomitant treatments, changes in the frequency or nature of assessments, hospitalization, or any other medically required intervention. Once an adverse event is detected, it should be followed until its resolution, and assessment should be made at each visit (or more frequently, if necessary) of any changes in severity, the suspected relationship to the study drug, the interventions required to treat it, and the outcome.

#### **7.4.4.2 Serious adverse events**

A serious adverse event (SAE) is an undesirable sign, symptom or medical condition which:

- is fatal or life-threatening
- results in persistent or significant disability/incapacity
- constitutes a congenital anomaly/birth defect
- requires inpatient hospitalization or prolongation of existing hospitalization, unless hospitalization is for:

- routine treatment or monitoring of the studied indication, not associated with any deterioration in condition (specify what this includes)
- elective or pre-planned treatment for a pre-existing condition that is unrelated to the indication under study and has not worsened since the start of study drug
- treatment on an emergency outpatient basis for an event not fulfilling any of the definitions of a SAE given above and not resulting in hospital admission
- social reasons and respite care in the absence of any deterioration in the patient's general condition
- is medically significant, i.e., defined as an event that jeopardizes the patient or may require medical or surgical intervention to prevent one of the outcomes listed above

To ensure patient safety, every SAE, **regardless of suspected causality**, occurring after the patient begins taking study drug and until 4 weeks after the patient has stopped study treatment must be reported to Pfizer immediately upon learning of its occurrence. Any SAEs experienced after this 4-week period should only be reported to Pfizer if the investigator suspects a causal relationship to the study drug. Recurrent episodes, complications, or progression of the initial SAE must be reported as follow-up to the original episode within 24 hours of the investigator receiving the follow-up information. An SAE occurring at a different time interval or otherwise considered completely unrelated to a previously reported one should be reported separately as a new event.

#### 7.4.5 Instructions for rapid notification of serious adverse events

The principal investigator has the obligation to report all serious adverse events to the FDA, IRB, and Pfizer.

All events reported to the FDA by the investigator are to be filed utilizing the Form FDA 3500A (MedWatch Form).

From the time that the subject receives the first dose of axitinib and including 28 calendar days after the last administration, **all events must be reported to Pfizer within 24 hours of learning of its occurrence. Furthermore, serious adverse events must be reported immediately upon awareness if the SAE is fatal or life-threatening**—regardless of the extent of available information.

Like an SAE, all other reportable events must be reported to Pfizer within 24 hours of awareness on an *IIR SAE Form* (or other agreed reporting method) and followed up to determine outcome, including the later occurrence of an associated SAE..

Any serious adverse event occurring after the patient has provided informed consent and until 4 weeks after the patient has stopped study participation must be reported to the Institutional Review Board.

Serious adverse events occurring more than 4 weeks after study discontinuation need only be reported if a relationship to the Pfizer study drug (or therapy) is suspected.

For Comparator Drugs/Secondary Suspects (Concomitant Medications), all serious adverse experiences will be forwarded to the product manufacturer by the investigator.

### **7.4.5.1 Pregnancies**

Any pregnancy that occurs during study participation should be reported. To ensure patient safety each pregnancy must also be reported to Pfizer within 24 hours of learning of its occurrence. The pregnancy should be followed up to determine outcome, including spontaneous or voluntary termination, details of the birth, and the presence or absence of any birth defects, congenital abnormalities, or maternal and/or newborn complications.

### **7.4.6 Laboratory evaluations**

Schedule and timing of all laboratory evaluations are listed in Table 3-4.

#### **Pregnancy Test**

A serum pregnancy test is required for all females of child-bearing potential within 7 days prior to the first dose of axitinib and during treatment.

#### **Hematology**

Hematology must include hemoglobin, hematocrit, platelets, total white blood cell count (WBC) and differential. PT (INR) evaluation will be mandatory at baseline only.

#### **Blood chemistry**

Blood chemistry must include a comprehensive metabolic panel (sodium, potassium, chloride, bicarbonate, calcium, glucose, creatinine, blood urea nitrogen, albumin, total protein, SGOT (AST), SGPT (ALT), total bilirubin, alkaline phosphatase), as well as magnesium and phosphorus.

#### **Urinalysis**

Standard urinalysis dipstick assessment (pH, protein, glucose, blood, ketones, and leukocytes) will be performed. This must be supplemented with laboratory quantification of any potentially relevant abnormalities.

#### **Sample Storage and Genetic Testing**

Samples will not be stored for future use and will not be used for genetic testing.

#### **7.4.6.1 Vital signs**

Vital sign assessment consists of height (first visit), pulse, blood pressure, respiration rate, temperature and weight. Blood pressure, pulse and respiration rate should be measured on patients after at least 3 minutes in the sitting position

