The nonclinical safety profile of axitinib has been well characterized through the conduct of single-dose and repeat-dose toxicity studies of up to 39 weeks in duration, and safety pharmacology, genetic toxicity, reproductive and developmental toxicity, and phototoxicity studies. The primary target organ toxicities were observed in the gastrointestinal, hematopoietic, musculoskeletal, and reproductive systems. Additionally, hemodynamic effects (elevated blood pressure, reduced heart rate) were identified from repeat-dosing in conscious, telemetered animals. Axitinib was not identified as a mutagen or clastogen, but considered an aneugen at area under the plasma concentration-time curve (AUC) exposure that exceeds that at the recommended human dose (RHD) of 5 mg BID. While axitinib has relevant ultraviolet (UV) absorbance with the potential to distribute to sun-exposed tissues, no phototoxicity potential was identified from in vitro testing in 3T3 fibroblasts. Many of the findings identified from non-clinical safety testing are consistent with the anticipated pharmacological response to a VEGF receptor inhibitor, including the blood pressure changes, and effects on ovarian follicles and the growth plate of actively growing animals, which are reliant on angiogenesis for development. Fertility and developmental effects were also observed, consistent with the effects identified from toxicity studies on reproductive organs and role of angiogenesis in the development of a fetus.

Axitinib and its metabolites were widely distributed into tissues in mice, but did not accumulate and were not retained for long periods of time in most tissues. The plasma protein binding was 97%, 98%, and 99% in the mouse, dog, and human, respectively.

In humans, the median recovery of [C] axitinib radioactivity in feces was 37.0% and in urine was 22.7% (total recovery = 59.7%) of the total orally administered dose (5 mg). In plasma, the glucuronide was the predominant metabolite and accounted for approximately 50% of the circulating radioactivity. The sulfoxide and unchanged parent drug accounted for approximately 20% of the circulating radioactivity. In feces, the parent drug represented the single most predominant radioactive component (12% of the dose).

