### *Pediatric Studies*

The Children's Oncology Group phase 1 study ADVL1315 (NCT02164838) for pediatric patients with recurrent/refractory solid tumors recently determined a recommended phase 2 dose (RP2D) of 2.4 mg/m^2 PO BID, corresponding to approximately 4mg PO BID in an average sized adult, or 80% of the adult standard starting dose [J Clin Oncol 34, 2016 (suppl; abstr 10558)]. In this study, oral axitinib tablets were administered twice daily, continuously in 28-day cycles. Dose levels 2.4 and 3.2 mg/m^2/dose were evaluated using a rolling 6 design. As of December 11, 2015, 17 patients were enrolled with 1 ineligible (inadequate time from prior therapy). The median age was 14 yrs (range 5–17 yrs); 9 were male. Patients received a median 3 prior chemotherapy regimens (range 1-8). Cancer diagnoses included soft tissue sarcomas (7), Ewing (2) and osteosarcoma (1), neuroblastoma (2), Wilms tumor (1), hepatoblastoma (1), hepatocellular carcinoma (1), medullary carcinoma (1), and epithelial-myoeithelial carcinoma (1). Toxicity data were available for 15 patients (6 at dose level 1, 5 at dose level 2, and 4 on an expanded PK cohort). One patient was inevaluable for toxicity due to inadequate drug exposure. DLTs occurred in 0/6 and 2/5 patients treated at dose level 1 and 2 respectively (palmar-plantar erythrodysesthesia syndrome (1); intratumoral hemorrhage (1)). Cycle 1 hematologic toxicities included grade 3 lymphopenia (1) and grade 1 or 2 anemia (4), lymphopenia (3), elevated hemoglobin (3), leukopenia (2), neutropenia (1), thrombocytopenia (1), and lymphocytosis (1). Non-hematologic toxicities included grade 1 or 2 nausea (5), hypertension (4), anorexia (3), creatinine elevation (2), diarrhea (2), fatigue (2), headache (2), lipase elevation (2), proteinuria (2), and acneiform rash (2). The most common subsequent cycle grade 3 or 4 toxicities included neutropenia (grade 3 (3), grade 4 (1)) and lymphopenia (grade 3 (1), grade 4 (1)).

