## 3 Research Strategy

**Primary Objective:** To estimate the objective volumetric response rates to axitinib in pediatric and adult NF2 patients with VS.

**Secondary Objectives:** To assess the toxicity of axitinib given daily in patients with NF2 and to examine the association of objective measures of response on MRI, i.e. volumetric tumor analysis with clinical measures of response, i.e. (audiogram), as well as quality of life assessments (NFTI-QOL). In addition, response in non-VS tumors, such as other schwannomas and meningiomas, may be explored.

**Drug Dosage and Administration (adult patients, age  $\geq$ 18 years):** 5 mg axitinib PO BID, with increase to 7 mg PO BID and 10 mg BID after 2 and 4 weeks, respectively, provided no adverse reactions (i.e., not exceeding grade 2 toxicities) and normotensive and not receiving antihypertension medications. Axitinib will be given continuously in 28-day cycles.

**Drug Dosage and Administration (pediatric patients, age <18 years):** 2.4 mg/m^2 axitinib PO BID, with increase to 3.2 mg/m^2 PO BID after 2 weeks, provided no adverse reactions (i.e., not exceeding grade 2 toxicities) and normotensive and not receiving antihypertensive medications. Axitinib will be given continuously in 28-day cycles using a dosing nomogram shown in Section 7.3.1. The maximal dose of 3.2 mg/m^2 PO BID exceeds the recommended phase 2 dose from the pediatric phase 1 trial, with the rationale that young NF2 patients, who

are generally not pre-treated with myelotoxic chemotherapy are likely to tolerate a higher dose of axitinib compared to the heavily pre-treated, refractory cancer patients enrolled on the pediatric phase 1 study [J Clin Oncol 34, 2016 (suppl; abstr 10558)]. Similar to adult patients on this study, the option to escalate the dose is intended to optimize secondary target inhibition and therefore increase the likelihood of responses.

**Study Assessments:** MRIs including volumetrics and audiograms at baseline and after every 3rd cycle (i.e. 12 weeks). Monthly study visits including H&P, neurological examination and standard laboratory evaluations. Quality of life assessments (NFTI-QOL) at baseline and cycle 6.

**Treatment Duration:** Until radiographic progression or unacceptable toxicity.

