#### 5 Proposed Sample Size and Timeline for Recruitment

A maximum of 17 evaluable subjects will be accrued to this study. According to our initial estimates, and based on our prior experience with lapatinib and everolimus phase 2 trials for adults and children with an average accrual rate of  $>2$  patients per month, the expected accrual period was approximately 12 months. However, the widespread use of bevacizumab on clinical trials and off-label, has rendered a large number of NF2 patients ineligible for this study, resulting in slower than expected accrual. The protocol was amended to include pediatric patients after pediatric phase 1 data became available, to increase enrollment.

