### Secondary

[figure not shown]
- To assess the toxicity of axitinib given daily in patients with NF2 and to examine the association of objective measures of response on MRI, i.e. volumetric tumor analysis with clinical measures of response, i.e. (audiogram), as well as quality of life assessments (NFTI-QOL). In addition, response in non-VS tumors, such as other schwannomas and meningiomas, may be explored.

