## **7.3 Treatment**

### **7.3.1 Axitinib administration**

The study drug axitinib will be self-administered. The investigator will instruct the patient to take the study drug exactly as specified in the protocol. Axitinib should be administered orally twice daily, approximately 12 hours apart, preferably in the morning and evening, at approximately the same time every day with or without food. Axitinib should be swallowed whole with a glass of water. If the patient vomits or misses a dose, an additional dose should not be taken. The next prescribed dose should be taken at the usual time.

Axitinib will be provided by Pfizer, Inc. Two strengths of tablets (1 mg and 5 mg) are being used in the clinical program and approved for use in those countries in which axitinib (Inlyta®) is marketed. All tablets contain common compendial excipients and film-coating materials. The tablets will be packaged in appropriate packaging material and stored at room temperature.

Axitinib PO will be taken continuously until disease progression or unacceptable toxicity, in continuous treatment cycles of 28 days each (maximum of 12 cycles):

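### Height is required at the first visit only, so the protocol secures no on-treatment height in children, although growth-plate effects were seen in growing animals

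*Combined protocol and SAP*

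**What the plan says.** Section 7.4.6.1 defines the vital signs: "Vital sign assessment consists of height (first visit), pulse, blood pressure, respiration rate, temperature and weight". Height is the only item tied to one visit. Table 3-4 repeats the vital-signs row at every visit but has no row for height, so the restriction in 7.4.6.1 governs.

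Section 1.1 lists, among nonclinical findings in keeping with VEGF receptor inhibition, "effects on ovarian follicles and the growth plate of actively growing animals".

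Children entered the trial late. Section 5 states: "The protocol was amended to include pediatric patients after pediatric phase 1 data became available, to increase enrollment". Section 7.2.2 sets the lower age limit at 5 years. Section 7.3.1 gives treatment "in continuous treatment cycles of 28 days each (maximum of 12 cycles", and a note under Table 3-4 provides for cycles beyond 12 on the same schedule.

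Height appears in one further place. Section 7.3.1 defines pediatric hypertension by a blood-pressure percentile that depends on age, height and sex, and a child must be normotensive to be escalated. The pediatric dose tables in the same section are indexed by BSA.

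Toxicity is a secondary objective in Section 6: "To assess the toxicity of axitinib given daily in patients with NF2".

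**The concern.** The protocol reports an effect on growing bone in animals, gives it a pharmacological explanation, and then enrolls growing patients without requiring a second height. A change needs two measurements, and only the first is secured. If sites do not happen to record later heights, the trial cannot list even a simple per-child change, and missed readings cannot be recovered afterwards.

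The pediatric experience cited in Section 1.1 does not close the gap. That phase 1 study covered the relevant ages ("The median age was 14 yrs (range 5–17 yrs); 9 were male"), with toxicity data from 15 patients. The listed toxicities include no growth finding, but the text does not say whether height was followed.

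A second, smaller issue concerns dosing. As a child grows, a first-visit height becomes outdated, yet the text allows it to be used for both the hypertension percentile and BSA.

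**Working it through.** The plan gives no figure on this point, so the check is mainly a reading of every place where a later height could be required.

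**Where a second height might come from**

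- *Vital signs (7.4.6.1, Table 3-4):* repeated at each visit, but height is restricted to the first.
- *Day 1 (note to Table 3-4):* baseline evaluations are repeated if more than 4 weeks have passed since screening. This is at drug dispensing, before treatment.
- *Visits (Section 3):* "Monthly study visits including H&P, neurological examination and standard laboratory evaluations". Section 7.4.6.2 names only a neurological examination as mandatory content.
- *Safety assessments (7.4.4) and specific toxicities (7.3.4):* no growth or bone monitoring. Thyroid function, hemoglobin, proteinuria and liver enzymes each have stated on-treatment monitoring.
- *Hypertension percentile and BSA tables (7.3.1):* both use height directly or through BSA; neither orders a new measurement.

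Protocol-required heights on treatment: 0 over 12 × 28 = 336 days (48 weeks, 0.92 year).

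**What repeated heights could show**

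Assumptions, not in the documents: a growing child gains 4 to 10 cm/year; one height reading has SD 0.3 to 0.5 cm; for illustration, a drug effect halves growth.

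- 95% measurement error of a change: 1.96 × √2 × 0.3 = 0.83 cm, to 1.96 × √2 × 0.5 = 1.39 cm.
- Week 12 (0.23 year): normal growth 0.92 to 2.30 cm; shortfall if halved 0.46 to 1.15 cm. This is mostly within the error.
- Week 24 (0.46 year): shortfall 0.92 to 2.30 cm. This overlaps the error range.
- Week 48 (0.92 year): normal growth 4 × 0.92 = 3.68 to 10 × 0.92 = 9.20 cm; shortfall 1.84 to 4.60 cm. This exceeds the error.

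Clearing measurement error is not enough. At week 48 halved growth (1.84 to 4.60 cm) overlaps normal growth (3.68 to 9.20 cm) between 3.68 and 4.60 cm. A gain in that interval fits either a slow normal grower or a fast grower slowed by half. Without prior growth velocity or pubertal stage the two cannot be told apart.

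**How far dosing is touched**

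The pediatric escalation can first occur after 2 weeks. With up to 4 weeks from screening to dispensing, the height is then at most about 6 weeks old: 10 × 6/52 = 1.2 cm of growth at the upper assumed rate. An outdated height matters more for later blood-pressure assessments and any later titration. For BSA, adjacent rows at dose level 0 (0.94–1.14 and 1.15–1.35 m²) differ by 1 mg/day, so the effect is confined to children near a boundary. Weight is measured repeatedly. The documents do not say when BSA is recalculated, so the size of any dose difference cannot be derived.

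**The case against.** The best case for leaving the text alone has four parts.

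1. *Sites will measure height anyway.* The percentile and BSA give them reason to, and monthly examinations and repeated weights continue. This is plausible, but the text does not require it, and both tools can be used with the first-visit value. A reader should not infer that children will go unmeasured; only that measurement is left to local habit.
2. *Adverse-event collection is broad.* Section 7.4.4.1 takes any undesirable sign found by any route. That stands in general, but slow loss of growth is hard to notice without a second height.
3. *The data would be weak.* There would be few children, no control group, and no information from adolescents who have stopped growing. This stands in full. Section 1.2 places hearing loss mostly in adolescence or young adulthood, which suggests few growing participants, although no age distribution is given. One might infer that a 48-week height would reveal a drug effect in an individual child; the overlap shown in the working rules that out.
4. *No objective or analysis names growth.* True, but toxicity is an objective, and growth is a plausible toxicity specific to the patients added by amendment.

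A reader might also infer from Section 1.1 that slowed growth is expected in children. The documents do not support that: the finding is in animals, no exposure level is given for it, and no growth data in children are reported. It makes an effect plausible and no more.

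**Conclusion.** The point holds as a minor, inexpensive safety improvement. The protocol requires zero on-treatment heights in children over 336 days or more, despite a nonclinical growth-plate signal. It also permits an outdated height in the pediatric hypertension percentile and BSA. This conclusion rests on the text alone. The growth rates, measurement SD and halving are assumptions, used only to show what the added readings can and cannot tell.

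The radiographic response endpoint, the 9 + 8 patient two-stage rule and its error rates are unaffected. Any influence on dosing is limited and cannot be sized from the documents; they give no ground for saying that children will be misdosed. Follow-up heights would permit a descriptive listing, but could not establish a shortfall in a single child or attribute one to axitinib.

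**What to change.** - In Section 7.4.6.1, replace *height (first visit)* with *height (first visit; in patients under 18 years also at the end of every third cycle, with the MRI visit, and at end of treatment)*.
- Add a Height row to Table 3-4 with an age footnote, as the NFTI-QOL row already has.
- State in Section 7.3.1 that blood-pressure percentiles and BSA use the most recent height.
- In Section 13, add a descriptive per-patient listing of change in height for those under 18, as part of the safety summary, with no test and no claim of causality.

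The timing follows the imaging schedule in Section 3: "MRIs including volumetrics and audiograms at baseline and after every 3rd cycle (i.e. 12 weeks". The end-of-treatment reading matters because treatment can stop early: a child stopping in cycle 5 would otherwise have only the week-12 value. Table 3-4 shows no end-of-treatment column, so this reading should be attached to the discontinuation visit or the safety follow-up in Section 7.4.4.

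The cost is one brief, non-invasive reading at four scheduled visits per child completing 12 cycles, plus one at end of treatment where that falls elsewhere. If all 17 evaluable patients were children, the scheduled readings would number 17 × 4 = 68. That is a guide and not a ceiling, since inevaluable children and cycles beyond 12 would add to it; the actual number of children is not given and is probably well below 17.
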